#### **Outcome measures**

**Participant eligibility and recruitment:** A log will be kept documenting the number of people with RA screened, ineligible, eligible, consented and declined. Feasibility outcomes will be reported on

- The proportion of screened people with RA who meet the inclusion criteria as a percentage of the total screened people
- The percentage of eligible participants that consented to be a part of the intervention

**Intervention adherence:** The user application will record the number of taVNS sessions started and completed. Adherence will be reported as a percentage of possible sessions completed prior to the final assessment (out of 14).

**Usability and Acceptability:** Individual items and total scores from both questionnaires will be evaluated. Overall acceptability of 60% or higher will be considered adequate, given the prototype design.

Adverse events/safety: Any participant withdrawals, reasons for withdrawal and any interventionemergent adverse events during the intervention period will be documented and reported both in absolute numbers and as a percentage out of 12 participants. An intervention-emergent adverse event (TEAE) will be considered any unfavourable and unintended sign (including an abnormal laboratory finding), symptom, or disease that occurs during the intervention period and may or may not be considered related to the intervention. During the Day 8 and Day 15 assessment sessions, participants will be asked the open question: 'Have you experienced any health problems or had any unusual symptoms or abnormal changes in bodily function in the last week?' If the participant answers yes, they will be asked to list any health problems/symptoms/changes in body function they have experienced, and a series of follow-up questions will be posed for each problem identified including: Can you describe it? When did it start? How long did it last for? How frequently did you experience it? Are you still experiencing it? Did it affect your usual daily activities? In what way? Did you seek any medical treatment? If so, what was this? This information will be used to create a TEAE log and then to classify and grade each TEAE using the Common Terminology Criteria for Coding Adverse Events (CTCAE).

**Estimates of mean intervention effect and variance**: Intervention effect sizes, using Cohen's d method [26], will be calculated from baseline to 7 sessions and baseline to 14 sessions for resting and grip pain intensity, pain interference, psychological distress, patient global assessment of disease activity, and health assessment questionnaire, SF36 pressure pain thresholds, resting vagal tone (RMSSD, HF-HRV) and inflammatory biomarkers (CRP, TNF- $\alpha$ , IL-1 $\beta$ , IL-10 and IL-17A).

**Relationships between HRV biomarkers and pain measures**: We will examine and report the relationships between changes in resting pain, grip pain, and pressure pain thresholds in each assessment

session (pre to immediately post 20 mins taVNS), and the change in each of the HRV parameters over the same time using Pearson correlation coefficients [27] or Spearman rank coefficients [28].

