#### Statistical Analysis:

Feasibility outcomes will be reported for

- **Participant eligibility and recruitment:** This will be reported based on the people with RA screened, ineligible, eligible, consented and declined.
- Intervention adherence: Reported by the number of sessions completed out of 14.

- Usability and Acceptability: Scores from usability and acceptability questionnaires will be evaluated.
- Estimates of mean intervention effect and variance: Intervention effect sizes will be calculated from baseline to 7 sessions and baseline to 14 sessions for the patient-reported scores, HRV parameters of RMSSD and HF-HRV and blood inflammatory biomarkers.
- Adverse events/safety: Safety-related events and withdrawals will be reported in absolute numbers and as a percentage out of 12 participants.
- **Relationships between HRV biomarkers and pain measures:** A correlation between changes in HRV and changes in pain and pain sensitivity will be reported.

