#### **Objectives**

- 1. To determine if a future single-centre clinical trial of home-based taVNS is feasible in people with RA. This will be determined by
  - a. Estimating the proportion of patients with RA that meet the eligibility criteria.
  - b. Estimating how many eligible patients can be recruited.
  - c. Estimating the intervention adherence based on the percentage of the taVNS sessions started and completed.

- d. Evaluating the usability challenges and acceptability of in-home use of the prototype system and the user application.
- e. Identifying any adverse events/issues related to safety.
- 2. To explore potential dose-response relationships by estimating the mean intervention effect and variance on
  - a. Pain intensity (resting visual analogue scale (VAS), gripping VAS)
  - b. Pain sensitivity (pressure pain threshold)
  - c. Pain interference (Brief Pain Inventory)
  - d. Psychological distress (Depression, Anxiety and Stress Scale [DASS-21])
  - e. Health assessment (PGA [patient global assessment of disease activity] and HAQ [health assessment questionnaire])
  - f. C-reactive protein (CRP), Tumor Necrosis Factor-α (TNF-α), Interleukin (IL)-1β, IL-10 and IL-17A
  - g. Resting vagal tone (RMSSD, HF HRV), based on the assessment after the 7th and the 14th session.
- To determine whether HRV is a feasible biomarker for a future closed-loop taVNS device, we will explore the relationships between immediate post-taVNS change in HRV parameters and pain and pain sensitivity measures.

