#### **Participants**

Twelve participants will be recruited from the Rheumatology outpatient departments in the Auckland region. This sample size is based on the number of participants that have been considered feasible to

recruit over 6 months rather than any formal power calculation. Participants will be included based on the following criteria:

- Aged 18 years and over
- Diagnosed with adult-onset RA according to ACR/EULAR 2010 RA classification criteria
- Have the presence of at least 3/28 swollen and/or at least 3/28 tender joints with 1 tender joint being in the hand or wrists

Participants will be excluded from the study if they have any of the following:

- Ear infection (otitis media or otitis externa)
- Poor hand dexterity and no access to a helper at home who could assist in fitting the in-ear taVNS device and the respiration sensor strap
- Changes in oral or biologic disease-modifying antirheumatic drugs (DMARDs) in the last 4 weeks
- Have had intraarticular or intramuscular corticosteroids within 2 weeks prior to study entry
- Unstable dosing regimen of NSAIDs or analgesics in the last 2 weeks
- History of arrhythmia, myocardial infarction in the last 12 months, currently on beta-blocker medication or history of stroke affecting the brainstem
- Previous vagotomy
- Currently implanted electrical and/or neurostimulator device
- Active malignancy or history of active malignancy in the last 2 years, with the exception of nonmelanoma skin carcinoma or carcinoma in situ
- Severe comorbidities which in the judgement of the study physicians would deem the participant not suitable as it may impact the safety of study conduct
- Known cognitive impairments
- Psychiatric illness with active psychosis
- Pregnant

Participants will be free to withdraw from this study at any time without affecting their right to receive further treatment. In addition, participants may be withdrawn after the initial assessment session(s) if the study team determines that they do not have sufficient finger dexterity to fit and operate the equipment at home or a person living with them who is able to assist them. Finally, participants may be withdrawn if the study physicians ([name], [name]) consider it inappropriate for them to continue for any reason, including intervention-emergent adverse events, a serious adverse event, or medical reasons unrelated to the study. Reasons for withdrawal will always be documented and reported.

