#### **Other treatments**

In addition to taVNS, participants will receive usual care as deemed appropriate by the study physicians ([name], [name]), provided this is stable in the 4 weeks leading up to the baseline assessment and throughout the 14-day intervention period. Usual care may include medications and other regular treatments deemed appropriate by the study physicians. Changes to existing medications (e.g. DMARDs, corticosteroids) will not be permitted during the 14-day intervention period.

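### The eligibility outcome is worded on the inclusion criteria alone and omits the 13 exclusions; separately, two sections give different stability windows for NSAIDs and analgesics

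*Protocol*

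**What the plan says.** Objective 1a, the first component of the primary feasibility objective, is "Estimating the proportion of patients with RA that meet the eligibility criteria".

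Under Outcome measures, the paragraph on eligibility and recruitment begins with the data source: "A log will be kept documenting the number of people with RA screened, ineligible, eligible, consented and declined". Two percentages follow. The first is "The proportion of screened people with RA who meet the inclusion criteria as a percentage of the total screened people". The second is "The percentage of eligible participants that consented to be a part of the intervention".

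The Statistical Analysis part of the synopsis describes the same outcome by its counts: "This will be reported based on the people with RA screened, ineligible, eligible, consented and declined".

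The Participants section gives 3 inclusion bullets and then, as a separate list, 13 exclusion bullets. The synopsis repeats both lists.

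On medication, one exclusion bullet in Participants is "Unstable dosing regimen of NSAIDs or analgesics in the last 2 weeks". Another sets 2 weeks for intraarticular or intramuscular corticosteroids, and a third sets 4 weeks for DMARD changes. The Other treatments section allows usual care "provided this is stable in the 4 weeks leading up to the baseline assessment" and says that usual care may include medications.

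**The concern.** The protocol keeps inclusion and exclusion criteria as distinct lists, so a numerator defined by the inclusion criteria is not the number eligible. Someone with three tender joints who takes a beta-blocker meets every inclusion criterion and cannot be enrolled, yet counts as a success in the first percentage as worded. The sentence is the operative definition for Objective 1a and does not measure what that objective asks for.

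A feasibility study reports these two percentages so that a later team can project screening numbers from them. The natural step is to multiply the share eligible by the share consenting. Here the first percentage ends at one group (inclusion criteria met) and the second starts from another (eligible), so the product is not the share of screened people who consent.

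The medication windows are a separate matter, but they bear on the same count because they decide who is eligible. Two screeners working from different sections could classify the same person differently.

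**Working it through.** **1. The outcome against the rest of the protocol**

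| Place | Group named |
|---|---|
| Objective 1a | those meeting the eligibility criteria |
| Outcome measures, screening log | screened, ineligible, eligible, consented, declined |
| Outcome measures, first percentage | those meeting the inclusion criteria, over all screened |
| Outcome measures, second percentage | consented, over eligible |
| Synopsis, Statistical Analysis | screened, ineligible, eligible, consented, declined |

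The first percentage is the only entry that names the inclusion criteria.

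**2. Direction and size if applied literally**

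Let S be the number screened, M those meeting all inclusion criteria, E those who also have no exclusion, and C those who consent. Let x be the share of M with at least one exclusion, so E = M(1 − x).

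- Literal outcome: M/S.
- Eligible proportion: E/S = (M/S)(1 − x).
- Ratio of literal to eligible: 1/(1 − x). This is never below 1, and equals 1 only when no exclusion removes anyone who met the inclusion criteria.
- Product of the two reported percentages: (M/S)(C/E) = (C/S) × 1/(1 − x). It exceeds C/S by the same factor.

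The protocol states no screening, eligibility or consent rate, so there is no figure of its own to reproduce. The 12 participants rest on what is feasible to recruit in 6 months, with no formal power calculation, and do not depend on this outcome.

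The table is therefore an illustration on assumed values: M/S of 40% or 60%, consent of 50%, and x from 0 to 50%. The number to screen for 12 recruited is 12 divided by (proportion × 0.5), rounded up.

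| M/S (reported) | x | E/S | Factor | Screen for 12, from the reported percentages | Screen for 12, actually needed |
|---|---|---|---|---|---|
| 40% | 0 | 40% | 1.00 | 60 | 60 |
| 40% | 10% | 36% | 1.11 | 60 | 67 |
| 40% | 30% | 28% | 1.43 | 60 | 86 |
| 40% | 50% | 20% | 2.00 | 60 | 120 |
| 60% | 0 | 60% | 1.00 | 40 | 40 |
| 60% | 10% | 54% | 1.11 | 40 | 45 |
| 60% | 30% | 42% | 1.43 | 40 | 58 |
| 60% | 50% | 30% | 2.00 | 40 | 80 |

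For example, at M/S = 40% and x = 30%: 12/(0.40 × 0.5) = 60, against 12/(0.28 × 0.5) = 85.7, rounded up to 86.

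**3. Medication windows**

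| Drug class | Participants (exclusions) | Other treatments | Conflict |
|---|---|---|---|
| DMARDs | 4 weeks | 4 weeks | No |
| NSAIDs, analgesics | 2 weeks | 4 weeks | Yes |
| Intraarticular or intramuscular corticosteroids | 2 weeks | 4 weeks, if they are usual care | Conditional |

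Counting both windows back from baseline, a person whose NSAID dose changed 15 to 28 days earlier passes the exclusion list and fails the condition in Other treatments. For corticosteroids, Other treatments names them among the existing medications that may not change during the 14 days. That points towards usual care but does not settle whether a single earlier injection breaks the 4 weeks of stability.

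**The case against.** The strongest reply is that the phrase about inclusion criteria is loose wording for eligibility. The sentence before it sets up a log with eligible and ineligible counts, the paragraph is about eligibility, Objective 1a says eligibility, and the synopsis reports from all the log categories. If those counts are published, any reader can compute E/S. This largely stands. It means the right data will exist and the overstatement is conditional on a literal reading. It does not make the defined percentage correct: the sentence is still the definition of a component of the primary objective, and it disagrees with every other statement of that component.

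Three stronger readings are tempting, and the documents do not support them.

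- A reader might infer that the reported proportion will certainly be too high, and by a large factor. Neither follows, because the log permits the correct figure and x is unknown.
- A reader might infer that particular exclusions, such as beta-blockers, recent drug changes or dexterity, will be the ones that limit recruitment. The protocol gives no frequency for any exclusion.
- A reader might infer that people later found unable to handle the device stay counted as eligible, since "participants may be withdrawn after the initial assessment session(s) if the study team determines that they do not have sufficient finger dexterity". No section says how they are counted in the eligibility proportion. Their withdrawals and reasons are to be reported, so they are not hidden. Reclassifying them as ineligible would be a preference, and it could move a device-handling failure, itself a feasibility result, out of view.

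On the medication windows, it is fair to say that the discrepancy affects only people with a relevant change in the third or fourth week before baseline. It would be too much to call the whole eligible population undefined, or to say that recent drug changes will enter the before-after comparison; that depends on which section governs.

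**Conclusion.** The outcome is wrongly worded. As written, it leaves 13 exclusions out of a measure that Objective 1a defines by eligibility, and its result cannot be multiplied by the consent percentage. If it is applied literally and at least one exclusion removes someone who met the inclusion criteria, the eligible proportion is overstated by 1/(1 − x). The direction is algebraic; the size cannot be found from the protocol.

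The window conflict is a second, independent inconsistency. It is definite for NSAIDs and analgesics, conditional for injected corticosteroids, and absent for DMARDs.

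Both should be corrected, but neither threatens the study. The counts needed for the right proportion are already to be logged, and the window conflict touches a limited set of candidates.

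**What to change.** - In Outcome measures, define the first percentage as the number of screened people who meet all inclusion and no exclusion criteria, divided by all screened. It then matches Objective 1a, the log and the synopsis, and chains with the consent percentage.
- Report the number ineligible by reason.
- Reconcile the Participants and Other treatments sections on medication stability, so that screeners apply one stated window per drug class, and state whether injected corticosteroids count as usual care. Which window applies is for the investigators to decide.

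The cost is a few lines of protocol text and, if the log does not already have it, a field for the reason for ineligibility. The reported eligibility will be equal to or lower than the figure under the present wording.

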#### **Study Design**

A single-arm, repeated measures feasibility study will be undertaken. Participants will receive 14 sessions of daily taVNS for 20 minutes. Two of these sessions will be supervised and take place at North Shore Hospital, as part of an assessment session, while 12 of these sessions will be completed unsupervised, in the participant's home. The participants will be required to visit North Shore Hospital for three 1-hour assessment sessions on day 1, day 8 and day 15, during which patient-reported outcomes, resting HRV, quantitative sensory testing and a blood sample of the participant will be collected for the evaluation of inflammatory biomarkers.

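### Adherence is scored out of 14 sessions, two of them supervised at hospital, so it is a poor match to a feasibility objective about home-based taVNS

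*Protocol*

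**What the plan says.** The adherence outcome is defined in two places, both with a denominator of 14. Outcome measures has: "Adherence will be reported as a percentage of possible sessions completed prior to the final assessment (out of 14". The synopsis, under Statistical Analysis, has: "Reported by the number of sessions completed out of 14".

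Study Design gives the make-up of the 14. The total is "Participants will receive 14 sessions of daily taVNS for 20 minutes". Of these, "Two of these sessions will be supervised and take place at North Shore Hospital", and "12 of these sessions will be completed unsupervised, in the participant's home".

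The primary objective is "To determine if a future single-centre clinical trial of home-based taVNS is feasible in people with RA". Adherence is the third of its five components (1a to 1e), worded as "Estimating the intervention adherence based on the percentage of the taVNS sessions started and completed". That component is not restricted to home sessions.

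Outcome measures also says, just before the reporting sentence, that the user application records both started and completed sessions. No section defines a percentage out of the 12 home sessions.

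**The concern.** The study is meant to show whether people with RA can and will use the device at home. The Day 1 session is the induction, where fitting of the electrode, pulse sensor and respiration strap is taught. The Day 8 session is supervised as part of an assessment visit. Completing either shows that the participant attended. It says little about setting up and running the kit without staff present.

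Putting these two sessions in the same percentage as the 12 home sessions mixes clinic attendance with home use. For participants who attend both visits, the effect is largest where home use is poorest. The adherence estimate is one of the figures a planner would carry into the future trial, so it should measure home use directly.

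**Working it through.** **Inputs**
- Denominator: 14 (Outcome measures; synopsis, Statistical Analysis).
- Supervised hospital sessions within the 14: 2 (Study Design).
- Unsupervised home sessions within the 14: 12 (Study Design).
- k, the home sessions completed, is not known in advance. The values below are illustrative and span 0 to 12.
- c, the clinic sessions completed before Day 15: 2, or 1 if only Day 1 is done.

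**The plan's own figure.** Day 1 (1) + Days 2–7 (6) + Day 8 (1) + Days 9–14 (6) = 14, which is also 2 + 12. The count reproduces. The supervised share is 2/14 = 14.3% of each participant's denominator, or 24 of 168 sessions across the 12 planned participants (2 × 12 and 14 × 12).

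**Formulas.** Reported adherence is (c + k)/14. Home adherence is h = k/12, so k = 12h.
- Both clinic sessions done: (2 + 12h)/14 − h = (2 − 2h)/14 = (2/14)(1 − h). This is never negative.
- Only Day 1 done: (1 + 12h)/14 − h = (1 − 2h)/14. This is positive below h = 50%, zero at 50% and negative above it.

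**Results** (reported adherence, with its difference from home adherence in percentage points)

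| Home sessions k | Home adherence k/12 | Both clinic sessions: (2 + k)/14 | Day 1 only: (1 + k)/14 |
|---|---|---|---|
| 0 | 0% | 14.3% (+14.3) | 7.1% (+7.1) |
| 3 | 25.0% | 35.7% (+10.7) | 28.6% (+3.6) |
| 6 | 50.0% | 57.1% (+7.1) | 50.0% (0) |
| 8 | 66.7% | 71.4% (+4.8) | 64.3% (−2.4) |
| 9 | 75.0% | 78.6% (+3.6) | 71.4% (−3.6) |
| 11 | 91.7% | 92.9% (+1.2) | 85.7% (−6.0) |
| 12 | 100% | 100% (0) | 92.9% (−7.1) |

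**A count to reconcile.** The synopsis Methods describe three combined assessment and intervention sessions plus another 12 at home, which makes 15, and Figure 2 also shows taVNS on Day 15. Study Design gives 14. If a Day 15 session entered the numerator over 14, a full completer would score 15/14 = 107.1%. The limit to sessions before the final assessment appears to exclude this, but the passages must be reconciled. The home count of 12 is the same in both descriptions.

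**The case against.** The strongest reply is that the measure fits its stated objective. Objective 1c concerns adherence to the intervention over all taVNS sessions, and Study Design defines that intervention as 14 sessions. Completed sessions over 14 is then the ordinary measure, applied alike in the synopsis and the main text, with its composition disclosed. This stands: a reader might infer that the outcome contradicts objective 1c, and it does not. What remains is that the objective above 1c is about home-based use and no figure isolates it.

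Four stronger readings are tempting and are not supported.
- *Adherence is always inflated.* Only the Day 1 session is close to certain for someone who starts. Day 8 needs a return visit, and the Participants section allows withdrawal after the initial session or sessions. With Day 8 missed and more than half of the home sessions done, the 14-session figure understates home adherence.
- *Started sessions are dropped.* The application records them under the same outcome, and objective 1c names them. The reporting sentence simply does not repeat the word, and their presentation can be left to an analysis plan.
- *The measure is undefined after withdrawal.* The stated 14 can be read as a fixed denominator, and further rules for withdrawals commonly belong in an analysis plan.
- *Failure would be hidden.* A participant with no home use who attended both visits would score 14.3%, which is plainly poor. Missed sessions also trigger reminders and, after two in a row, a call. Usability and acceptability of home use are asked about on Day 15.

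**Conclusion.** The point holds as a mismatch between the adherence measure and the home-based aim. It is neither an internal contradiction nor an error in the count of 14.

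Its size is modest. When both clinic sessions are completed, the reported figure is above home adherence by at most 14.3 points, by 7.1 points at half home use and by 3.6 points at three-quarters, and the gap closes at full home use. When only Day 1 is completed, the difference runs from +7.1 to −7.1 points. These figures rest on the 2 + 12 split in Study Design and on assumed values of home use.

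A reader might infer that a feasibility decision would flip. The protocol does not support that: it states no adherence threshold, and its only numeric adequacy criterion of this kind is the 60% for acceptability. Adherence is also one of five components of the primary objective. What changes is the estimate passed to the future trial. The change is worth making because it is better aimed at the study's question and costs almost nothing.

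**What to change.** Under Outcome measures, and in the matching line of the synopsis:
- Define home adherence as home sessions completed out of 12, for all enrolled participants who start the intervention. Keep 12 as the denominator after withdrawal.
- Keep in that denominator anyone withdrawn before taking the kit home, and list them separately as set-up failures. The Participants section allows withdrawal for insufficient dexterity without a helper, so limiting the outcome to those who took the kit home would remove some of the failures it should count.
- Report home sessions started out of 12 beside it, since objective 1c names both started and completed.
- Keep completed sessions out of 14 as a measure of total exposure.

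The cost is a few sentences of wording. The application already records sessions started and completed, so no new data collection is needed, provided its log lets the Day 1 and Day 8 sessions be told apart from the home sessions. The one downside is that the reported adherence may be slightly less favourable.

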After the first assessment session, participants will carry the equipment kit home. This kit will include the prototype system with a finger pulse sensor, a respiration belt, a commercial taVNS (Vagustim) device, a tablet running the mobile application and alcohol wipes. The finger pulse sensor and respiration belt have been chosen after the completion of a prior study conducted from April to July 2023 at Auckland University of Technology's North Shore campus. This study was approved by the AUT ethics committee. It recruited 35 participants who wore these sensors along with additional sensors for a duration of 60 to 90 minutes. The finger pulse sensor demonstrated excellent correlation (> 97%) and acceptable accuracy (24% error margin), with 95% confidence intervals and a p-value of < 0.001, in measuring the participant's heart rate variability when compared to a 12-lead electrocardiogram (ECG) system. The respiration belt achieved a true positive rate of 85%, with 95% confidence intervals and a p-value of < 0.001, in measuring the sensoring the start of exhalation when compared to a gold standard respiration belt. These sensors will be housed in the sensor box shown in the following figure.

The participant will be required to complete 12 further 20-minute sessions at the rate of 1 session/day over the next 14 days and return to the North Shore Hospital laboratory for 2 more occasions for assessments, with the equipment kit. Participants will be provided with the researcher's contact details for any kind of technical support or other assistance required.

Figure 1. Participant kit containing a 10-inch mobile tablet, Vagustim device with custom left ear electrode, sensor box with connections to finger sensor, respiration belt and power bank.

Treatment adherence, including completion of daily sessions, will be automatically captured by the mobile application. If participants miss a single session, a follow-up text message and email will be sent reminding them to complete the next session as planned. If participants fail to complete 2 consecutive sessions, a follow-up phone call will be made by a member of the study team to encourage adherence and troubleshoot any issues with the training. A phone number and email address will be made available for participants to seek technical assistance throughout the intervention.

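### The structured adverse-event question is asked only of those who attend Day 8 and Day 15, so the safety rate out of 12 can be too low if anyone withdraws or misses a visit

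*Protocol*

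**What the plan says.** The adverse events paragraph of the protocol's Outcome measures section sets out one structured enquiry: "During the Day 8 and Day 15 assessment sessions, participants will be asked the open question". The question reads "Have you experienced any health problems or had any unusual symptoms or abnormal changes in bodily function in the last week", and a positive answer leads to follow-ups on onset, duration, frequency, effect on daily life and treatment sought. The paragraph continues: "This information will be used to create a TEAE log and then to classify and grade each TEAE". Withdrawals, their reasons and events are to be "documented and reported both in absolute numbers and as a percentage out of 12 participants".

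Three other places bear on the point:
- **Participants.** "Participants will be free to withdraw from this study at any time without affecting their right to receive further treatment". Adverse events are among the grounds on which a study physician may withdraw someone, and "Reasons for withdrawal will always be documented and reported".
- **Study Procedures.** After two consecutive missed sessions, "a follow-up phone call will be made by a member of the study team to encourage adherence" and to deal with problems with the training. Participants also receive contact details for assistance.
- **Roles and responsibilities.** The study physicians take part in identifying and coding adverse events, and the primary investigator ensures that they are reported.

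No section describes a health enquiry for a participant who has withdrawn or missed a visit.

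**The concern.** Identifying adverse events and safety issues is item 1e of the primary objective. Twelve of the sessions take place unsupervised at home with a prototype, so staff do not see most of the exposure and the log depends on what participants are asked or choose to report.

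The asking depends on attendance, but the denominator does not. A participant who was not asked stays in the 12 and adds to the numerator only if an event reaches the team by another route. Because the protocol itself names adverse events as a possible ground for withdrawal, those not asked may differ from those asked. This is a matter of data collection: a later analysis cannot recover answers that were never sought.

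**Working it through.** **Inputs from the protocol.** Question at Day 8 and Day 15; recall of one week; denominator 12 (Outcome measures). The sample size rests on feasible recruitment, with no power calculation (Participants). There is no planned safety rate to reproduce, and no dropout, missed-visit or event rate is given. Those values below are assumptions.

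**Step 1. Which weeks does the question reach?**

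| Attendance | Week 1 asked | Week 2 asked |
|---|---|---|
| Both visits | yes | yes |
| Withdraws before Day 8 | no | no |
| Attends Day 8, then withdraws or misses Day 15 | yes | no |
| Misses Day 8, attends Day 15 | no | yes |

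The last row follows from the recall period: at Day 15 the question looks back one week and does not reach the first.

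**Step 2. Effect of one missed participant.** A participant whose only event is captured by no route lowers the percentage by 1/12 = 8.3 points. A participant with another event already in the log still counts, so the participant-level rate does not move, although the event count does.

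**Step 3. Same risk in everyone.** Let *p* be the true proportion with an event and *k* the number asked at neither visit, with none of their events captured otherwise. The expected reported rate is *p* × (12 − *k*)/12.

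| Assumed *p* | *k* = 1 | *k* = 2 | *k* = 3 |
|---|---|---|---|
| 10% | 9.2% | 8.3% | 7.5% |
| 25% | 22.9% | 20.8% | 18.8% |
| 40% | 36.7% | 33.3% | 30.0% |

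For *p* = 25% and *k* = 2: 0.25 × 10/12 = 20.8%, which is 4.2 points low. For *k* = 0 the shortfall is zero.

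**Step 4. Higher risk in the unasked.** Assume 25% in those asked and 50% in the 2 not asked. The true expected rate is (10 × 0.25 + 2 × 0.50)/12 = 3.5/12 = 29.2%. The expected report is still 20.8%, so it is 8.3 points low.

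**Step 5. Extreme case.** Suppose 3 of the 10 asked report an event and both unasked participants had one that was not captured. The report is 3/12 = 25.0% and the truth 5/12 = 41.7%.

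**Step 6. A result of no events.** The one-sided 95% upper limit is 1 − 0.05^(1/n). It is 22.1% for n = 12 and 25.9% for n = 10. Quoting zero out of 12 when 10 were asked overstates what was ruled out.

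**The case against.** A reader might infer that events are collected only through the visit question and that anyone who withdraws or misses a visit is never asked. The document does not support that. Outcome measures commits to documenting any emergent event in the intervention period, and its definition includes abnormal laboratory findings, which a spoken question cannot supply. Someone who leaves after Day 8 has already answered for week 1, and someone who misses one visit is still asked at the other. Only a participant who attends neither visit is not put the question at all.

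The other routes also count. An event that causes withdrawal should appear as the recorded reason. A physician who withdraws a participant because of an adverse event knows of it. The call after two missed sessions could bring device discomfort to light, and participants can contact the team. Withdrawals are reported beside the events, and nothing says that an unasked participant is classified as having had none.

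A reader might also take 25% against 42% as the expected error. It is a worst case: both unasked participants have an event and every other route fails. With 12 participants, sampling error is far larger than most of these shifts: the exact 95% interval for 3/12 runs from 5.5% to 57.2%.

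All of this narrows the point, but a gap remains. None of these routes is a structured health enquiry. A withdrawal reason is not an open question with follow-ups that support grading, and it does not help when a visit is missed without withdrawal. The call has adherence and troubleshooting as its stated purpose. The Roles and responsibilities section says who handles events, not how they are elicited from people who are not attending.

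**Conclusion.** The point holds in a conditional form. Followed as written, the plan leaves one or both weeks without structured questioning for anyone who withdraws or misses a visit, while the denominator stays at 12. What can be lost are events that neither cause withdrawal nor are volunteered or found by another route. Any error from this source is downward.

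Its size depends on dropout and event rates that the protocol does not give. Over the assumed range of 1 to 3 unasked participants and a uniform true rate of 10% to 40%, the expected shortfall runs from 0.8 points (10% − 9.2%) to 10 points (40% − 30%). These figures assume that no other route captures the events of the unasked, so actual losses may be smaller. This does not invalidate the study, but it is worth correcting before data collection because it touches part of the primary objective.

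**What to change.** Add to the adverse events paragraph of Outcome measures, with a cross-reference in Study Procedures:

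> Any participant who withdraws, or who misses the Day 8 or Day 15 visit, will be asked the same open question and follow-up questions by telephone within a stated number of days. The question will also be asked in the call made after two consecutive missed sessions. In each case it will cover the whole period since the participant was last asked.

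The recall period needs that change: if the wording stays at one week, a late call would leave the same gap. Beside the rate out of 12, report the number of participants with complete event ascertainment.

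The cost is a short script added to a call the team already makes, plus a few extra calls at most. Some withdrawn participants may decline, and the reported number with complete ascertainment will then show how much is missing. No treatment or clinical rule changes.
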